## **2. STUDY OBJECTIVES, ENDPOINTS AND HYPOTHESES**

### **2.1. Objectives**

The primary objective of this study is to demonstrate that AO1D is non-inferior to habitual lenses with respect to the change in contact lens subjective comfort from baseline to 2-week follow-up in a population of symptomatic daily disposable contact lens wearers.

The secondary objectives of this study are to demonstrate that AO1D is non-inferior with respect to the (1) change in contact lens related dry eye symptoms, (2) to subjects' habitual lenses with respect to contact lens related dry eye symptoms and (3) subjective comfort at 2-week follow-up in a population of symptomatic daily disposable contact lens wearers.

This study is conducted with the primary intent to support the market claims on the AO1D.

# Clinical Study Protocol

## Johnson & Johnson Vision Care, Inc.

### 2.2. Endpoints

#### Primary Endpoint

- Change in CLUE Comfort score from baseline to 2-week follow-up

Subjective overall vision and comfort scores will be assessed using Contact Lens User Experience (CLUE) questionnaire. CLUE is a validated patient-reported outcomes questionnaire to assess patient-experience attributes of soft, disposable contact lenses (comfort, vision, handling, and packaging) in a contact-lens wearing population in the US, ages 18-65. Scores follow a normal distribution with a population average score of 60 (SD 20), where higher scores indicate a more favorable/positive response. A 5-point increase in an average CLUE score translates into 10% shift in the distribution of scores for population of soft disposable contact lens wearers.

#### Secondary Endpoints

- Change in CLDEQ-8 total score from baseline to 2-week follow-up
- CLDEQ-8 total score at 2-week follow-up
- CLUE Comfort score at 2-week follow-up

The CLDEQ-8 is a validated outcome measure for soft contact lenses wearers. It has been highly correlated with habitual baseline status and change in overall opinion when subjects are refit with contact lenses. A CLDEQ-8 total score of  $\geq 12$  is proposed to identify contact lens wearers who could benefit from clinical management of their contact lens related symptoms. A three points change in CLDEQ-8 total scores has also been shown to be clinically important. This study will include the symptomatic subjects who will have a CLDEQ total score of  $\geq 15$ .

#### Tertiary Endpoints

1. CLDEQ-8 Questions: CLDEQ-8 individual questions will be analyzed only if primary and/or secondary endpoints are met.
  - During a typical day in the past 2 weeks, how often did your eyes feel discomfort while wearing your contact lenses?
  - When your eyes felt discomfort with your contact lenses, how intense was this feeling of discomfort (on a scale of 1-5) at the end of your wearing time?
  - During a typical day in the past 2 weeks, how often did your eyes feel dry?
  - When your eyes felt dry, how intense was this feeling of dryness (on a scale of 1-5) at the end of your wearing time?
2. CLUE Comfort Questions: CLUE comfort questions will be analyzed only if primary and/or secondary endpoints are met.
  - These contact lenses were very comfortable (C001\_2)
  - I could wear these contact lenses comfortably for as long as I wanted to (C008\_1)
  - These lenses were very comfortable at the end of the day (C020\_2)
  - My eyes felt very dry at the end of the day (C021\_2)
  - My eyes felt dry all day (C022\_1)
  - My eyes felt dry at the end of the day (C023\_1)

# **Clinical Study Protocol**

## **Johnson & Johnson Vision Care, Inc.**

- I have experienced dry eyes (C041\_1)
  - The comfort of these lenses decreased throughout the day (C061\_1)
3. CLUE Vision Questions:
- I had very good vision at the end of the day (V004\_2)
  - I experienced fluctuations in the quality of my vision (V009\_1)
  - I was very satisfied with the quality of my vision in dim lighting (V013\_2)
  - I was satisfied with the quality of my vision at night (V014\_1)
  - I was very satisfied with the clarity of distant objects (V034\_2)
  - I was satisfied with the clarity of near objects (V035\_1)
  - I was very satisfied by the clarity of my vision at the end of the day (V037\_2)
  - My vision with these lenses was exceptional (V124\_3)
4. MRD Questions:
- These lenses help to reduce the feeling of dryness at the end of the day (MIS01977)
  - I would recommend them to people who experience dryness with their own contact lenses (P3\_0021\_p10)
  - Have you been able to use these lenses for 8 hours or more with digital devices? (MIS01978)
- Please think about your experience with your current contact lenses/ the study contact lenses. Please indicate how you would rate the contact lenses on each of the following characteristics.
- Not making your eyes feel dry throughout the day (P3\_0006\_p38)
  - Keeping your eyes from feeling dry at the end of the day (P3\_0006\_p39)
- Please indicate how often, if ever, you experienced the following sensations when you wore your current contact lenses/ the study contact lenses.
- Burning (P3\_0023\_p01)
  - Dryness (P3\_0023\_p02)
  - Grittiness (P3\_0023\_p03)
5. Preference Questions:
- Thinking about the last two lenses you tried, which lens did you prefer overall? (PREF1)
  - Overall Comfort (PREF10\_3)
  - Comfort at the end of the day (PREF10\_5)
  - Overall vision (PREF10\_7)
  - Keeping your eyes from feeling dry (PREF10\_14)

Other Endpoints:

Average Wear Time / Comfortable Wear Time

# **Clinical Study Protocol**

## **Johnson & Johnson Vision Care, Inc.**

### **Safety Endpoints:**

Adverse events, lens fitting characteristics, slit lamp findings, entrance/exit visual acuity, subject reported ocular symptoms

### **2.3. Hypotheses**

Primary Hypothesis:

The Primary hypothesis will be evaluated between the two study arms; only the first period will be considered for the second study arm.

| Primary Hypotheses |   |
|--------------------|---|
| Endpoint           | Hypothesis  |
| CLUE Comfort       | The Test lens will be non-inferior to the Habitual lens with respect to the change in CLUE comfort score from baseline at 2-week follow-up. A non-inferiority margin of -5 points on the CLUE scale will be used. |

Secondary Hypotheses:

The primary hypothesis must be met in order to test the secondary hypotheses. The secondary hypothesis regarding the change in CLDEQ-8 Scores will be evaluated between the two study arms; only the first period will be considered for the second study arm. The remaining two secondary hypotheses will be evaluated within the second study arm only.

| Secondary Hypotheses          |  |
|-------------------------------|--|
| Endpoint                      | Hypothesis   |
| Change in CLDEQ-8 Total Score | The Test lens will be non-inferior to the Habitual lens with respect to the change in CLDEQ-8 total score from baseline at 2-week follow-up. A non-inferiority margin of 3 points on the CLDEQ-8 scale will be used. |
| CLDEQ-8 Total Score           | The Test lens will be non-inferior to the Habitual lens with respect to CLDEQ-8 total score at 2-week follow-up. A non-inferiority margin of 3 CLDEQ-8 points will be used.  |
| CLUE Comfort                  | The Test lens will be non-inferior to the Habitual lens with respect to CLUE comfort score at 2-week follow-up. A non-inferiority margin of -5 CLUE points will be used.   |

The primary hypothesis must be met in order to satisfy the objective of the study.

# **Clinical Study Protocol**

## **Johnson & Johnson Vision Care, Inc.**

### **Tertiary Hypotheses:**

Tertiary hypotheses will be evaluated in the following manner.

1. If the primary hypothesis is not met, then the tertiary hypotheses will not be evaluated.
2. If the primary and secondary hypotheses are met: All tertiary hypotheses will be evaluated for both between the study arms and within the second arm.
  - a. If the primary and secondary hypotheses regarding CLUE comfort are met then the tertiary hypotheses relevant to this endpoint will be evaluated for both between the study arms and within the second arm.
  - b. If only the primary hypothesis for CLUE comfort is met then, then associated tertiary hypotheses relevant to this endpoint will only be evaluated between study arms.
  - c. If both secondary hypotheses regarding CLDEQ8-Scores are met, then the tertiary hypotheses relevant to this endpoint will be evaluated for between the study arms only and within the second arm.
  - d. If only 1 of the secondary hypotheses regarding CLDEQ8-scores is met, then the associated tertiary hypotheses relevant to this endpoint will be evaluated between study arms.

| Tertiary Hypotheses |   |
|----------------------------|---|
| Endpoint            | Hypothesis   |
| CLDEQ-8 Questions          | 
The Test lens will be non-inferior to the Habitual lens with respect to the following CLDEQ-8 individual questions at 2-week follow-up. An odds ratio margin of 0.67 will be used.
 

1. During a typical day in the past 2 weeks, how often did your eyes feel discomfort while wearing your contact lenses?

2. During a typical day in the past 2 weeks, how often did your eyes feel dry?

3. When your eyes felt discomfort with your contact lenses, how intense was this feeling of discomfort (on a scale of 1-5) at the end of your wearing time?

4. When your eyes felt dry, how intense was this feeling of dryness (on a scale of 1-5) at the end of your wearing time?

 |

**Clinical Study Protocol**  
**Johnson & Johnson Vision Care, Inc.**

| Tertiary Hypotheses    |   |
|------------------------|---|
| Endpoint               | Hypothesis  |
| CLUE Comfort Questions | 
The Test lens will be non-inferior to the Habitual lens with respect to the following CLUE comfort individual questions at 2-week follow-up. An odds ratio margin of 0.67 will be used.
 
 
1. These contact lenses were very comfortable (C001_2)
 
2. I could wear these contact lenses comfortably for as long as I wanted to (C008_1)
 
3. These lenses were very comfortable at the end of the day (C020_2)
 
4. My eyes felt very dry at the end of the day (C021_2)
 
5. My eyes felt dry all day (C022_1)
 
6. My eyes felt dry at the end of the day (C023_1)
 
7. I have experienced dry eyes (C041_1)
 
8. The comfort of these lenses decreased throughout the day (C061_1)
 
   |
| CLUE Vision Questions  | 
The Test lens will be non-inferior to the Habitual lens with respect to the following CLUE vision individual questions at 2-week follow-up. An odds ratio margin of 0.67 will be used.
 
 
1. I had very good vision at the end of the day (V004_2)
 
2. I experienced fluctuations in the quality of my vision (V009_1)
 
3. I was very satisfied with the quality of my vision in dim lighting (V013_2)
 
4. I was satisfied with the quality of my vision at night (V014_1)
 
5. I was very satisfied with the clarity of distant objects (V034_2)
 
6. I was satisfied with the clarity of near objects (V035_1)
 
7. I was very satisfied by the clarity of my vision at the end of the day (V037_2)
 
8. My vision with these lenses was exceptional (V124_3)
 
 |
| MRD Questions          | 
The Test lens will be non-inferior to the Habitual lens with respect to the following MRD individual questions at 2-week follow-up. An odds ratio margin of 0.67 will be used.
 
 
1. These lenses help to reduce the feeling of dryness at the end of the day (MIS01977)
 
2. I would recommend them to people who experience dryness with their own contact lenses (P3_0021_p10)
 
3. Have you been able to use these lenses for 8 hours or more with digital devices? (MIS01978)
 
4. Not making your eyes feel dry throughout the day (P3_0006_p38)
 
5. Keeping your eyes from feeling dry at the end of the day (P3_0006_p39)
 
6. Burning (P3_0023_p01)
 
7. Dryness (P3_0023_p02)
 
8. Grittiness (P3_0023_p03)
 
   |

# **Clinical Study Protocol**

## **Johnson & Johnson Vision Care, Inc.**

| Tertiary Hypotheses  |  |
|----------------------|--|
| Endpoint             | Hypothesis   |
| Preference Questions | 
The Test lens will be superior to the Habitual lens with respect to the preference questions at 2-week follow-up:
 

• Based on your overall opinion of both study lenses, do you prefer one lens more than the other? (PVC015_1)

• Overall Comfort (PREF10_3)

• Comfort at the end of the day (PREF10_5)

• Overall vision (PREF10_7)

• Keeping your eyes from feeling dry (PREF10_14)

 |

### **3. TARGETED STUDY POPULATION**

#### **3.1. General Characteristics**

Approximately 112 potential subjects will be enrolled via pre-screening, and approximately 80 subjects (40 per arm) are targeted to complete the study. Subjects, ages 18-59 that are current daily disposable spherical soft contact lens wearers are to be enrolled in this clinical study.

Subjects will be pre-screened to determine symptomatology and targeted for enrollment with a \ questionnaire (APPENDIX F). Subjects whose daily disposable lens is the same as the test lens, ACUVUE OASYS®1-Day will not be eligible.

Recruitment will aim to enroll subjects evenly by habitual lens type by site. Considering subject availability and regional differences as potential barriers to the exact proportion of 20% per lens type by site, the maximum for each habitual lens type will be capped at 40% per lens type by site

#### **3.2. Inclusion Criteria**

Potential subjects must satisfy all of the following criteria to be enrolled in the study:

Inclusion Criteria after Screening:

1. The subject must read, understand, and sign the STATEMENT OF INFORMED CONSENT and receive a fully executed copy of the form.
2. Appear able and willing to adhere to the instructions set forth in this clinical protocol.
3. Between 18 and 59 (inclusive) years of age at the time of screening.
4. Be a daily disposable current soft contact lens wearer in both eyes with a minimum of 6 days/week wear time over the last 1 month by self-report.
5. Have a CLDEQ-8 score of 15 or greater with the habitual lens.
6. Subjects must possess a pair of spectacles for distance correction.

# **Clinical Study Protocol**

## **Johnson & Johnson Vision Care, Inc.**

7. Subject's habitual lens must be the following lens types: Alcon DAILIES® Aqua Comfort Plus®, Alcon DAILIES TOTAL1®, CooperVision® clariti® 1 day, CooperVision® MyDay®, or Johnson & Johnson 1-Day ACUVUE® Moist.

Inclusion Criteria after Baseline:

8. The subject's vertex corrected spherical distance refraction must be in the range of -1.00 D to -6.00 D (inclusive) in each eye.
9. The magnitude of subject's vertex corrected refractive cylinder must be less than 1.00 diopter in each eye.
11. Have spherical best corrected visual acuity of 20/25 or better in each eye.

### **3.3. Exclusion Criteria**

Potential subjects who meet any of the following criteria will be excluded from participating in the study:

Exclusion Criteria after Screening:

1. Subject's habitual lens is ACUVUE OASYS®1-Day.
2. Currently pregnant or lactating, by self-report.
3. Any ocular or systemic allergies, disease or use of medication which may interfere with contact lens wear (at the discretion of the investigator).
4. Any active ocular abnormalities/conditions that may interfere with contact lens wear (at the discretion of the investigator).
5. Any infectious diseases (e.g. hepatitis, tuberculosis) or a contagious immunosuppressive disease (e.g. HIV), by self-report.
6. Any corneal distortion resulting from previous hard or rigid gas permeable contact lens wear.
7. Habitual contact lens wear modality as extended wear ( $\geq 1$  night per month of extended wear).
8. Habitual contact lens is rigid gas permeable, toric, monovision or multi-focal.
- 9.. Any previous, or planned (during the course of the study) ocular surgery (e.g., radial keratotomy, PRK, LASIK, etc.).
10. Participation in any contact lens or lens care product clinical trial within 2 weeks prior to study enrollment.
11. Employee or employee's immediate family member of clinical site (e.g., Investigator, Coordinator, Technician).
12. Current habitual use of Restasis, Xiidra, ocular steroids, or any medication (Rx or over the counter (OTC)) that may interfere with contact lens wear (at the discretion of the investigator).

Exclusion Criteria after Baseline:

13. Any ocular allergies, infections or other ocular abnormalities that are known to interfere with contact lens wear and/or participation in the study. This may include, but not be limited to entropion, ectropion, extrusions, chalazia, recurrent styes, glaucoma, history of recurrent corneal erosions, aphakia, or corneal distortion.

# **Clinical Study Protocol**

## **Johnson & Johnson Vision Care, Inc.**

14. Any Grade 3 or greater biomicroscopy findings (this includes, corneal edema, corneal staining, corneal vascularization, conjunctival injection, tarsal abnormalities, bulbar injection) on the FDA classification scale [REDACTED]

### **3.4. Enrollment Strategy**

Study subjects will be recruited from the Institution/clinical site's subject database and/or utilizing Independent Ethics Committee (IEC) or Institutional Review Board (IRB) approved materials. Subjects will be pre-screened via phone or e-mail to determine symptomatology and targeted for enrollment with a CLDEQ-8 questionnaire score of 15 or greater. Recruited subjects will be habitual contact lens wearers of 5 difference lenses; Alcon DAILIES® Aqua Comfort Plus®, Alcon DAILIES TOTAL1®, CooperVision® clariti® 1 day, CooperVision® MyDay®, or Johnson & Johnson 1-Day ACUVUE® Moist. Further details about allocation between habitual lens types within clinical sites is located in Section 4.3.

## **4. STUDY DESIGN AND RATIONALE**

### **4.1. Description of Study Design**

This is a multi-site, randomized, bilateral, dispensing, parallel design study with two arms (ARM 1 and ARM 2). Subjects will be pre-screened for contact lens related dryness symptoms via phone or email prior to enter the study.

Subjects in ARM 1 will be fitted into AO1D and followed up after 2 weeks of wear. Subjects will be masked to the identity of the lens assigned. There will be 2 visits as follows:

- Pre-screen questions via. phone or email
- Visit 1: Screening, baseline evaluation, fitting AO1D
- Visit 2: 2-week follow up and final evaluation

Subjects in ARM 2 will be first fitted into their habitual lenses and dispensed for 2 weeks. At the follow-up visit, subject will be fitted into AO1D and followed up after 2 weeks of where. Subjects will not be masked to their habitual lens (open label), but they will be masked to the identity of AO1D during the second period of wear. There will be 3 visits as follows:

- Pre-screen questions via phone or email
- Visit 1: Screening, baseline evaluation, fitting habitual lens
- Visit 2: 2-week habitual lens follow up; fitting AO1D
- Visit 3: 2-week AO1D follow up and final evaluation

### **4.2. Study Design Rationale**

This study is a parallel design with two arms (ARM 1 and ARM 2). Subjects in the ARM 1 will receive the over labeled AO1D to wear bilaterally for about 2-weeks, while subject in ARM 2 will first receive the open labeled habitual lens to wear bilateral for approximately 2-weeks during the first wear period, then receive the over labeled AO1D in a bilateral fashion for approximately 2-weeks during the second wear period. This design will allow comparison

# **Clinical Study Protocol**

## **Johnson & Johnson Vision Care, Inc.**

of the Test lens against subjects' habitual lenses in both between the two study arms and within the ARM 2. The primary endpoints will compare the two study arms in a parallel design setting

The secondary endpoints within ARM 2 are to compare subject's habitual lenses and AO1D lenses. This study design allows efficient comparison of the Test lens compared to subjects' habitual lens with minimal sample size, as well as allows subjects to experience both lens types in efficient comparison.

### **4.3. Enrollment Target and Study Duration**

Approximately 112 potential subjects will be targeted to be enrolled via pre-screening, and approximately 80 subjects (40 per arm) are targeted to complete the study. Subjects will be considered enrolled in the study upon execution of informed consent.

Recruitment will aim to enroll subjects evenly by habitual lens type by site. Considering subject availability and regional differences as potential barriers to the exact proportion of 20% per lens type by site, the maximum for each habitual lens type will be capped at 40% per lens type by site. This will need to be monitored by the clinical site and clinical operations.

Depending on the study arm, there are 2 to 3 planned study visits and the study will last approximately 4 months, including approximately a 4-month enrollment period. Subjects who are discontinued prior to the final evaluation may be replaced at the discretion of the study sponsor.

## **5. TEST ARTICLE ALLOCATION AND MASKING**

### **5.1. Test Article Allocation**

This will be a randomized 2-arm study. This study is parallel design with 2 arms such that the first arm (refer as "ARM 1") is designed with 1 lens (the AO1D) while the second arm (refer as "ARM 2") is designed with 2 lenses wearing (habitual lens and AO1D) respectively. Subjects in the ARM 1 will receive the AO1D in a bilateral fashion for approximately 2 weeks, while the subjects in ARM 2 will first receive the open labeled habitual lens to wear bilaterally for approximately 2 weeks during the first wear period and then receive the AO1D to wear bilaterally for approximately 2 weeks during the second wear period.

Subjects will be randomly assigned to either ARM 1 or ARM 2 based on a computer-generated randomization schedule prepared before the study initiation. The randomization scheme will be generated using the PROC PLAN procedure from Statistical Analysis System (SAS) Software Version 9.4 or higher (SAS Institute, Cary, NC) provided by the study biostatistician.

The study site must follow the randomization scheme provided and complete enrollment per the randomization list and not pre-select or assign subjects. The randomized assignment of subjects will be performed at the first visit prior to the first fitting. The following must have occurred prior to randomization:

# **Clinical Study Protocol**

## **Johnson & Johnson Vision Care, Inc.**

- Informed consent has been obtained
- Subject meets all the inclusion / exclusion criteria
- Subject history and baseline information has been collected.

### **5.2. Masking**

This study will be a subject-masked to the Test lens. Subjects will be unaware of the identity of the Test lens as the Test lens will be over labeled. Due to the nature of the study design, each subject will be aware of the identity of the Control lens as it is her/his habitual lens. Investigators and clinical site personnel involved in the data collection may be aware of the identity of the investigational product.

Subjects who have had their treatment assignment unmasked are expected to return for all remaining scheduled evaluations. If necessary, subjects who are discontinued may be replaced to reach the subject completion target.

### **5.3. Procedures for Maintaining and Breaking the Masking**

One randomization code (alphanumeric character) per test article will be assigned by the study biostatistician using the form [REDACTED]. For ARM 2, one randomization code will be used for subjects' habitual lens regardless of the lens brand and type. Upon database lock, the study biostatistician will release the randomization codes to the data management.

When dispensing test articles, the following steps should be followed:

1. Investigator or designee (documented on the Delegation Log) will consult the lens fitting schedule/randomization scheme to obtain the test article assignment for that subject prior to dispensing.
2. Investigator or designee will record the subject's number on the appropriate line of the randomization scheme.
3. Investigator or designee will pull the appropriate test articles from the study supply. All test articles that are opened, whether dispensed (placed/fit on eye or dispensed outside the clinical site) or not, must be recorded on the Test Article Accountability Log in the "Dispensed" section.

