## 6.4. Packaging and Labeling

The test articles will be packaged in blisters, as the primary packaging. The Test lens will be over labeled to mask the subject to the identity of the lens. The Control lens will be open label. The study articles will be in investigational cartons sealed with a tamper evident seal, commercial cartons, or in plastic bags as the secondary packaging form. The sample study labels are shown below:

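### Sites allocate from a supplied randomisation list and no described step hides upcoming assignments, so the between-arm comfort comparison is open to selection bias

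*Combined protocol and SAP*

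**What the plan says.** Section 5.1 assigns subjects to an arm "based on a computer-generated randomization schedule prepared before the study initiation". The instruction to sites reads: "The study site must follow the randomization scheme provided and complete enrollment per the randomization list and not pre-select or assign subjects". The section then lists what must come before randomisation: consent, history and baseline data, and the condition "Subject meets all the inclusion / exclusion criteria". Section 7.2 has the same order, with eligibility confirmed at Step 1.15 and randomisation at Step 1.16.

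Section 5.3 gives the mechanics. The investigator or a delegate "will consult the lens fitting schedule/randomization scheme to obtain the test article assignment for that subject prior to dispensing", then enters the subject's number "on the appropriate line of the randomization scheme" and pulls the lenses from the study supply. On coding: "For ARM 2, one randomization code will be used for subjects' habitual lens regardless of the lens brand and type".

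On masking, Section 5.2 states: "Investigators and clinical site personnel involved in the data collection may be aware of the identity of the investigational product". Section 6.4 adds: "The Control lens will be open label".

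Section 14.5 compares the change in CLUE comfort between ARM 1 and the first period of ARM 2, on the per-protocol population.

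**The concern.** Randomisation protects a between-arm comparison only if whoever decides that a subject enters cannot foresee that subject's arm. Here the people who judge eligibility may also be the people who read the list. If they can see that the next line is ARM 1, they can admit, decline or defer the subject in front of them in light of that knowledge.

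The endpoint makes this matter. It is a self-reported comfort score, collected over two weeks from subjects who know when they are wearing their own lens. The result is meant to support market claims (Section 2.1). If subjects with more room to improve went preferentially to ARM 1, the estimated difference would favour the Test lens without any lens effect. Both the non-inferiority test and the follow-on superiority test would be affected.

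**Working it through.** This is mainly a matter of reading the sections together; no figure in the plan is challenged.

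**1. Form of the allocation tool.** Section 5.1 has the schedule prepared in advance, supplied to the site and followed as a list. Section 5.3 has site staff look up the assignment and write on one of its lines. Together these describe a list of several lines, worked at the site. No central or interactive release, sealed envelope or other covering of unused lines is described. Block size and stratification are not stated.

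**2. Do the codes conceal the arm?** There is one code per test article and a single code for all habitual lenses. Staff must then hand over either an over-labelled Test lens or the subject's own brand, and send the subject down a two-visit or a three-visit path. With two arms, one allocation is enough to show which code goes with which arm. Holding the code key until database lock keeps it from data management, not from the person pulling lenses.

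**3. Does the order of steps conceal the arm?** Step 1.15 before Step 1.16 controls when an assignment is made. It does not control when the line can be read.

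**4. Where is there room for judgement before Step 1.16?** Exclusions 3, 4 and 12 (Section 3.3) are at the investigator's discretion. At Step 1.14, a subject with a Grade 3 finding may return once more at the investigator's discretion, which can change that subject's place in the enrolment order.

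**5. Can the analysis repair it?** The model in Section 14.5 contains arm, time and their interaction, with age and gender optional. Working with change from baseline removes differences in starting level, but not differences in expected change. The ITT analysis keeps the groups as allocated, including any imbalance created at allocation.

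**6. Sensitivity of the primary test.** Inputs from Section 14.2: SDs 25.21 and 18.12, two-sided alpha 0.05, 80% power, effect 9, 40 per arm. The margin is -5 (Section 2.3).

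- SE = sqrt((25.21² + 18.12²)/40) = sqrt(963.88/40) = 4.91.
- Distance from the margin = 9 + 5 = 14. The Satterthwaite t-test then needs 40 per arm, with power 80.3%, which matches Table 9. Enrolment is 80 × 1.4 = 112, also as stated.
- With the true difference at the margin and a shift b favouring the Test lens, the one-sided error is 1 − F(t_crit; df, b/SE), where F is the noncentral t distribution function.

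| Assumed shift b (CLUE points) | One-sided error |
|---|---|
| 0 | 2.5% |
| 1 | 3.9% |
| 2 | 6.0% |
| 3 | 8.7% |
| 5 | 17.0% |

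Every non-zero b is an assumption. The table shows how the test would respond to a shift; it says nothing about whether one would occur.

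**The case against.** The strongest reply is that the documents show an undescribed concealment method, not an open list. Section 5.3 speaks of the appropriate line, not the next one, and nowhere says that unused lines can be read. The form used for the codes is redacted, and the scheme itself is a separate document. Section 13.4.1 lets the investigator break the code when medically necessary, which implies that sites work from codes. This stands as far as it goes: a reader might infer that staff do see upcoming assignments, and the text does not establish that. It does not remove the point, because the procedure as written contains no step that would prevent it.

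A reader might also infer that the ban on pre-selection is the sole protection. It is not. Consent, eligibility and baseline must come first, and there are also the delegation log, the accountability log, EDC audit trails and monitoring. These govern conduct and order, and leave a trail, but none hides an assignment.

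Investigator approval at Step 1.25 might be read as part of the same weakness. It comes after randomisation, so it concerns attrition and not concealment, and the change proposed here would not touch it.

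Finally, room for selection is limited. The CLDEQ-8 threshold rests on the subject's own answers, and lens type, age, refraction and acuity limits are fixed. One can also ask how staff would predict a two-week change. They cannot do so with precision, but they know the CLDEQ-8 score from Step 1.6, because they apply the cut-off of 15. Table 8 shows historical mean changes from -2.8 (n = 5, baseline 54.8) to 22.6 (n = 8, baseline 27.1). These are very small samples, but they suggest that expected change can vary with starting level.

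**Conclusion.** The point holds as an open risk in the allocation procedure. Followed as written, Sections 5.1 and 5.3 place a list at the site whose codes cannot separate knowledge of the arm from the people judging eligibility, and they describe nothing that withholds later assignments. The primary comparison between arms is therefore exposed to selection bias.

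The size of that bias cannot be estimated from the documents, and the shifts tabulated above are not estimates of it. The conclusion assumes that no concealment step sits in a document outside this one. If one does, stating it in Section 5.1 would settle the matter. The documents do not support a claim that staff will see the list ahead of time, that any steering will take place, or that the sample size is wrong. Because the remedy is cheap and the comparison at risk is the primary one, the change is worth making.

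**What to change.** In Sections 5.1 and 5.3, replace consultation of the site list with release of one assignment at a time, only after eligibility at Step 1.15 has been recorded. Two ways are practical:

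- sequentially numbered, opaque, sealed envelopes, opened in order, with date and time logged; or
- release through the EDC system named in Section 15.1, if it supports this. That section describes data capture only, so the capability needs to be confirmed.

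Keep the full list and any block size with the study biostatistician, and say so. Because staff can recognise the arm after each allocation, a known block size could make later assignments predictable even with envelopes.

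The cost is a set of envelopes per site or some EDC configuration, and a wording change in two sections. No additional subjects or visits are needed.
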